**The anti-inflammatory effect of prophylactic macrolides on children with chronic lung disease: a double blinded RCT**

**NCT02544984**

**Version date: 10/09/2015**

## **Research Aims**

### **Primary Aims:**

1. To determine if prophylactic use of azithromycin will reduce the total number of unscheduled face-to-face physician visit for respiratory related illness in a clinic, urgent care, emergency room or hospital setting during the 3-6 month study period, and subsequent 2 months follow-up.

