## **Study Design and Methods**

### *Overview:*

This pilot randomized control trial (RCT) will enroll 92 children from 6 months to <6 years of age that have chronic lung disease (CLD) such as bronchopulmonary dysplasia during two seasons of respiratory illnesses defined as 1st October to 31st March of each year (2015-2016 Season and 2016-2017 Season). If the minimum number of patients (n=92) in Season 1 is achieved, we will then perform an interim analysis of the data. These children will all be patients who receive their primary medical care from either the High Risk Children Clinic or the similar High Risk Infant Clinic that cares for premature infants from discharge until age 2. Clinic records will be screened to determine eligibility. Patients that have parental consent will be given a baseline EKG, a nasal aspirate, an oscillometer reading (over 2 years of age only), and a three to six month supply of either the medication or the placebo at an initial study visit. Both medications will be taken once a day for three days a week: Monday, Wednesday and Friday. The azithromycin medication will be dosed at 5 mg/kg/day. Adjustments in dosage amount will be made with any new weights obtained during the trial period. Any child that is eligible to receive Palivizumab will be given this every 28-30 days in clinic as per usual care. Patients will be followed on a monthly basis and closely monitored for adverse reactions; this will occur by phone, in clinic during their regularly scheduled appointments, and/or during any necessary illness visits. Any children with adverse reactions will discontinue the medication, but will continue to be followed clinically. At any clinic visit in which a child presents with respiratory infections, including pneumonia,

upper respiratory illness, bronchiolitis, etc., he/she will have an additional nasal aspirate and/or tracheal aspirate if applicable and an oscillometer reading (only for children >2 years) performed. At the completion of the 3-6 months treatment phase, each child will have a final nasal aspirate and/or tracheal aspirate if applicable, and an oscillometer reading performed. Data will continue to be collected for the following 2 months (April 1st to May 31st), to monitor for respiratory illnesses and possible side effects.

*Study Population:*

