#### *Study Procedures:*

Patients will be randomized by the REDCap statistical program in a double blind manner. Parents will then be provided with a medication or placebo for the duration of the study. Patients would be recruited for this study on a rolling basis from October 1st to December 31st, and all patients completing the intervention part of the protocol on 31st March at the end of the season. Half of the patients will receive azithromycin at a

dose of 5 mg/kg to be given once a day on Monday, Wednesday, and Friday. The other half, the control group, will be provided with a placebo medication of similar taste, color, texture, and consistency, also to be taken once a day on Monday, Wednesday, and Friday. Both the study medication and the placebo will be dispensed from Corner Compounding Pharmacy, mixed with a fish-oil base to ensure a shelf life of more than six months, and flavored with citrus to improve palatability. Parents will be contacted biweekly, either in clinic or by phone, to monitor for any adverse reactions, including rash, nausea, vomiting, diarrhea, or abdominal cramping. If a significant adverse reaction occurs, the medication will be discontinued. If an allergic reaction (such as rash or shortness of breath) is noted, the blind will be broken by Research Coordinator [name], who is not involved with the project. This un-blinding will be done to note if it is an allergy to the medication.

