## **Data Analysis Plan**

Patients will be randomized to one of two different branches by the REDCap data base randomization program. This will be a double-blind placebo controlled study. Standard frequentist and Bayesian analyses will be performed using an intent-to-treat approach. Total hospital days, total ER visits (counting one day for each ER visit), and unscheduled clinic visits (counting one day for each visit) for respiratory symptoms will be analyzed and related to treatment (Azithromycin vs Placebo), with logistic regression models and the treatment group as a covariate and random intercept to account for within patient correlation (due to multiple ED visits). To assess the probability of benefit, we will use Bayesian hierarchical models with interaction terms between treatment groups (Azithromycin vs Placebo) and predefined potential moderators. The groups will be stratified by palivizumab use and by tracheostomy on chronic mechanical ventilation. The conservative Bayesian approach of Dixon and Simon allows us to shrink the subgroup estimates to the overall mean treatment effect. For all Bayesian analyses, prior distributions for main effects will be neutral  $\sim N(0,1000)$ , and Uniform (0,1000) for SD parameters. Neutral and skeptical priors will be used for interaction terms. Point estimates of treatment effect and 95% credible intervals will be reported along with probability of treatment benefit.

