## **Sample size and power**

Based on data from our HRCC, we expect the control group to have 1.6 encounters per child-year (SD=1.66). Assuming a two-sided alpha = 0.05, a sample size of 90 (45/group) will have 80% power to detect a difference of 1 in the encounter rate between placebo and azithromycin groups (i.e., 1.6 vs 0.6 in encounter rate or 38% reduction). Power will be more limited for secondary outcomes but Bayesian analyses will provide an estimate of the probability of benefit in these outcomes.

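### Encounter totals are modelled with no observation-time term, although children are observed for 153 to 244 days and the sample size is set on a rate per child-year

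*Combined protocol and SAP*

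**What the plan says.** - **Outcome.** The Primary Aims ask whether azithromycin "will reduce the total number of unscheduled face-to-face physician visit for respiratory related illness", counted "during the 3-6 month study period, and subsequent 2 months follow-up". Study Outcomes also speaks of encounters and numbers of visits, and items 1a to 1c there cover the 3-6 month period only.
- **Entry and end of treatment.** Study Procedures: "Patients would be recruited for this study on a rolling basis from October 1", closing on 31 December, "and all patients completing the intervention part of the protocol on 31" March.
- **End of counting.** Overview: "Data will continue to be collected for the following 2 months (April 1st to May 31". The Risks section instead ties the two months of monitoring to the last azithromycin administration.
- **Analysis.** The Data Analysis Plan takes total hospital days, ER visits and unscheduled clinic visits and relates them to treatment "with logistic regression models and the treatment group as a covariate and random intercept to account for within patient correlation". The Bayesian models add moderators and interactions. Neither part names an offset, person-time or length of follow-up.
- **Sample size.** Sample size and power works in encounters per child-year and targets a "difference of 1 in the encounter rate between placebo and azithromycin groups".
- **Children who stop the drug.** The Overview says that they remain under clinical follow-up. No section gives a dropout allowance or says how a child who withdraws or cannot be reached is analysed.

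**The concern.** The design quantity has a time denominator and the analysed quantity does not. On the plain reading, a child who enters on 31 December, or whose family is lost after a month, contributes a low total that the model cannot tell apart from a low encounter rate. If one arm has less observed time, it shows fewer encounters with no drug effect. This is separate from the choice of a logistic model, because a count model without a time term would have the same gap. At stake is whether the primary estimate, and the Bayesian probability of benefit built on it, measures a difference in encounter rate or partly a difference in how long children were watched.

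**Working it through.** **1. The plan's own figure.** Inputs from Sample size and power: SD 1.66, difference 1.0 per child-year, two-sided alpha 0.05, power 80%.

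n per arm = 2 × (1.96 + 0.842)² × 1.66² / 1² = 2 × 7.85 × 2.756 = 43.3, so 44. The t-test version gives 44.2, so 45 per arm and 90 in total. The stated 90 is reproduced, in units of a rate per child-year.

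**2. Counting time.** Days from entry, both end dates included:

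| | Enter 1 Oct | Enter 31 Dec | Ratio |
|---|---|---|---|
| To 31 May, season 1 | 244 | 153 | 1.59 |
| To 31 May, season 2 | 243 | 152 | 1.60 |
| To 31 March, season 1 | 183 | 92 | 1.99 |
| To 31 March, season 2 | 182 | 91 | 2.00 |

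At 1.6 per child-year, a control child in season 1 is expected to have between 1.6 × 153/365.25 = 0.67 and 1.6 × 244/365.25 = 1.07 encounters, depending only on entry date.

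**3. Staggered entry alone.** Assume entry uniform over the 92 days and 46 children per arm (92 enrolled). SD of observed time = √((92² − 1)/12) = 26.6 days. The 95% range for the difference in mean time between arms is 1.96 × 26.6 × √(2/46) = 10.9 days.

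- Treatment plus two months: 10.9 / 198.5 = 5.5%.
- Treatment only: 10.9 / 137.5 = 7.9%.

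This is chance imbalance, centred on zero. In simulation (negative binomial counts, 1.6 per year, dispersion (1.66² − 1.6)/1.6² = 0.451, 46 per arm, no loss), the SD of the log ratio is 0.273 for totals and 0.271 for rates, a gain of about 1%. At 1.6 vs 0.6 per year with 45 per arm, simulated power is 84% for totals and 85% for rates.

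**4. Loss that differs by arm.** The documents give no loss rate, so these are assumptions: no drug effect, and loss at a uniformly random time, so that a lost child contributes half its time on average. Ratio of totals = (1 − ½ × loss on azithromycin) / (1 − ½ × loss on placebo).

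| Loss, azithromycin vs placebo | Ratio of totals | Ratio of rates (simulated) |
|---|---|---|
| Equal | 1.00 | about 1.00 |
| 15% vs 5% | 0.925/0.975 = 0.949 (simulated 0.949) | 1.000 |
| 20% vs 5% | 0.900/0.975 = 0.923 (simulated 0.920) | 0.997 |

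With loss confined to the azithromycin arm at 10%, 20% and 30%, the ratio of totals is 0.95, 0.90 and 0.85. The chance of a false significant result favouring azithromycin is then 3.7%, 5.4% and 7.8%, against 2.5% with no loss. A rate analysis stays at about 2.6-2.7%. These error rates use a t-test on per-child totals as a stand-in, because the planned logistic model is not specified closely enough to simulate. Loss concentrated on placebo would push the ratio the other way.

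**5. Where observed time should end.** If a lost child's time is closed at its last illness encounter, exposure depends on the outcome. Under the same assumptions and no drug effect, the rate ratio becomes about 1.04 (15% vs 5%) and 1.07 (20% vs 5%). Closing at the last scheduled contact gives about 1.00.

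**The case against.** **Rolling entry is harmless on average.** This stands. A reader might infer from the 153-244 day range that staggered entry biases the trial. It does not: randomisation balances entry date in expectation, and the ±5.5% is already part of the sampling error. A log-ratio SD of 0.273 means a 95% range of about 0.59 to 1.71 with no effect at all.

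**Intolerance does not end observation.** A reader might also infer that more children will be lost on azithromycin through side effects, so that the plan favours the drug. The documents do not support that. The Overview keeps following children who stop the drug, the analysis is by intention to treat, the children receive primary care in the study clinics, and Study Procedures schedules biweekly contact. What remains open is withdrawal, loss of contact, and the Risks section's two months after the last dose. Applied to early stoppers, that wording would make observed time depend on tolerance.

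**The plan may intend a rate.** The power section speaks of an encounter rate, and a logistic model with one record per child-day would carry exposure implicitly. That is possible, but the Data Analysis Plan defines no such unit and speaks of totals. A random intercept handles correlation within a child and does not adjust for time at risk. Anyone replacing the logistic model would have to settle exposure anyway, which is a reason to write it down now.

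**The benchmark matters.** An apparent reduction of 5-8% is 26-40% of the 20% expected in Study Outcomes, but only about 8-13% of the 62.5% reduction implied by 1.6 vs 0.6. Both comparisons are fair, and the documents do not settle which effect is the target.

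**Conclusion.** The point holds as a gap in specification with a conditional consequence. The plan names no observation-time term although counting time varies about 1.6-fold by design (2-fold on treatment) and the sample size is set on a rate. Staggered entry by itself costs about 1% in precision and causes no systematic error. Systematic error needs observed time that differs by arm, which the Overview limits and no section rules out. Its size, a ratio of totals of about 0.95 or 0.92, rests entirely on the assumed loss of 15% vs 5% or 20% vs 5% at random times. With equal loss it is nil. The documents do not show that such loss will occur or which arm it would favour. The change is worth making because it removes this dependence at almost no cost and puts the analysis in the same units as the sample size.

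**What to change.** 1. In the Data Analysis Plan, include log(days observed) as an offset in the primary count analysis and its Bayesian version, so that the treatment effect is a rate ratio.
2. Define days observed as randomisation to 31 May or, for a child lost earlier, to the last study contact (scheduled biweekly contact or visit, whichever is later), not the last illness encounter. Confirm that dated contacts continue through April and May, which Study Procedures does not say.
3. Reconcile the Overview and the Risks section on when counting ends for children who stop the drug early.
4. Report person-time and encounters per child-year by arm.
5. State the outcome in the Primary Aims and Study Outcomes as a rate.

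**Cost.** One derived variable and some wording. The sample size is unchanged. The offset assumes a roughly constant encounter rate over the counting period, which a season or calendar-month term can relax. It removes the person-time part of the error only. It does not correct for loss that is itself related to a child's illness.

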## **Sample size and power**

Based on data from our HRCC, we expect the control group to have 1.6 encounters per child-year (SD=1.66). Assuming a two-sided alpha = 0.05, a sample size of 90 (45/group) will have 80% power to detect a difference of 1 in the encounter rate between placebo and azithromycin groups (i.e., 1.6 vs 0.6 in encounter rate or 38% reduction). Power will be more limited for secondary outcomes but Bayesian analyses will provide an estimate of the probability of benefit in these outcomes.

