## **Study Outcomes**

1. In the treatment group, we expect a 20% total reduction in face to face encounters (defined as unscheduled sick visits, emergency room visits, and hospital admissions) for respiratory symptoms with the prophylactic use of azithromycin, as compared to the control group.
  - a. In the treatment group, we expect to have a 20% decrease in the number of unscheduled sick visits due to respiratory illness during the 3-6 month study period with the prophylactic use of azithromycin, as compared to the control group .
  - b. In the treatment group, we expect to have a 20% decrease in the number of Emergency Room visits due to respiratory illness during the 3-6 month study period with the prophylactic use of azithromycin, as compared to the control group.

- c. In the treatment group, we expect to have a 20% reduction in the number of hospital admissions due to respiratory illness during the 3-6 month study period with the prophylactic use of azithromycin, as compared to the control group.
2. In the treatment group, we expect a 10% total reduction (as compared to baseline) in the level of myeloperoxidase in the nasopharyngeal secretions collected during respiratory illnesses that require a face to face provider encounter, as compared to the control group.
3. In the treatment group, we expect a 10% total reduction in the level of pro-inflammatory cytokines in the nasopharyngeal secretions collected during respiratory illnesses that require a face to face provider encounter, as compared to the control group.
4. In the treatment group, we expect a 10% reduction from baseline in the level of airway obstruction as measured by a tremoFlo Airwave Oscillometry System during the 3-6 month study period, respiratory illness and at the conclusion of the intervention phase.
5. We expect no significant difference in adverse side effects between the treatment group receiving the macrolide and the control group receiving the placebo during the 4 month study.
6. We expect the intervention to be cost-effective from a healthcare system perspective.

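### The 80% power figure rests on a full child-year with no exposure term, while each child is observed for 5 to 8 months, and the plan's expected 20% reduction has only about 9 to 14% power

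*Combined protocol and SAP*

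**What the plan says.** Under Sample size and power the inputs are annual: "we expect the control group to have 1.6 encounters per child-year (SD=1.66". The test setting is given as "Assuming a two-sided alpha = 0.05", and the claim is that "a sample size of 90 (45/group) will have 80% power to detect a difference of 1 in the encounter rate". The effect is then written out as "i.e., 1.6 vs 0.6 in encounter rate or 38% reduction". The section mentions neither follow-up time nor an exposure adjustment, and it does not say over what period the SD was measured.

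The primary aim counts visits over 3-6 months of treatment plus 2 months. Study Procedures explains the range: "Patients would be recruited for this study on a rolling basis", from 1 October to 31 December, with all treatment ending on 31 March. The Overview adds: "Data will continue to be collected for the following 2 months", to 31 May. A child entering on 1 October is therefore observed for 8 months, and one entering on 31 December for 5.

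Study Outcomes gives a different effect size: "In the treatment group, we expect a 20% total reduction in face to face encounters".

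**The concern.** The power calculation and the outcome are on different time bases. At 1.6 per child-year and an even rate, a control child has 1.6 × 5/12 = 0.67 to 1.6 × 8/12 = 1.07 encounters in the window, and the planned difference of 1 becomes 0.42 to 0.67. Fewer events per child mean less information, so under any fixed variance model power is lower than the same model gives for a year.

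The same paragraph also holds effect sizes that do not agree with each other or with Study Outcomes. The stated power is what a reader would use to interpret a non-significant result. If 80% is taken at face value, such a result could be read as evidence against an effect that the trial had little chance of detecting.

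**Working it through.** **Inputs.** Control rate 1.6 per child-year, SD 1.66, 45 per group, two-sided alpha 0.05, difference 1 (Sample size and power); observation 5 to 8 months (Primary Aims, Overview, Study Procedures); 20% reduction (Study Outcomes). Assumptions, since the plan is silent: the rate is even over the year, the SD is that of a one-year count, and mean observation is (5 + 8)/2 = 6.5 months if enrolment is uniform.

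**Step 1: reproduce the plan.** Two-sample t test with noncentrality d / (s × √(2/n)) = 1 / (1.66 × √(2/45)) = 2.86 on 88 degrees of freedom gives power 0.807. The normal approximation gives 0.815. The 80% is thus a full-year comparison of two means with a common SD.

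**Step 2: put it on the observation window.** With f = months/12 the difference is f × 1. The plan gives no rule for scaling the SD, so several are shown.

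- A, variance proportional to time, common SD: s = 1.66 × √f.
- B, gamma-Poisson (negative binomial) with the control-arm SD in both arms. Dispersion k = (1.66² − 1.6)/1.6² = (2.756 − 1.6)/2.56 = 0.451; s² = m + k·m² with m = 1.6f.
- C, as B, but each arm has the variance implied by its own mean, averaged.
- D, negative binomial rate ratio, Wald test on the log scale: standard error = √{[1/(1.6f) + k + 1/(0.6f) + k]/45}.

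Power for 1.6 versus 0.6, 45 per group (t test for A to C):

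| Convention | 5 months | 6.5 months | 8 months | 12 months |
|---|---|---|---|---|
| A | 0.45 | 0.55 | 0.64 | 0.81 |
| B | 0.56 | 0.64 | 0.70 | 0.81 |
| C | 0.73 | 0.82 | 0.87 | 0.94 |
| D | 0.74 | 0.83 | 0.89 | 0.96 |

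Worked example, B at 6.5 months: m = 0.867, s = √(0.867 + 0.451 × 0.867²) = 1.10, difference 0.542, noncentrality 0.542/(1.10 × √(2/45)) = 2.34, power 0.64.

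A simulation of negative binomial regression with an exposure offset (46 per arm, exposure uniform on 5 to 8 months, 1500 runs) gave 0.87, consistent with D.

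**Step 3: the expected 20% reduction.** The difference is 0.20 × 1.6 = 0.32 per child-year. Over 5 to 8 months, power is 0.09-0.11 (A), 0.10-0.12 (B), 0.11-0.14 (C) and 0.11-0.14 (D). With a full year it is 0.15 by the plan's method and 0.16 under C. The simulation gave 0.14 for 5 to 8 months and 0.18 for a year. By the plan's method, 80% power would need 423 per arm even with a full year.

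**Step 4: the printed 38%.** (1.6 − 0.6)/1.6 = 62.5%. The ratio 0.6/1.6 is 0.375, so the label may be the fraction remaining. Alternatively, 1.6 versus about 1.0 may have been meant. The 80% fits only the difference of 1: a true 38% reduction (0.38 × 1.6 = 0.61, about 0.6) has power 0.40 with a full year by the plan's method, and about 0.20 to 0.32 pro-rated under A and B.

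**The case against.** A reader might infer from the time-base mismatch that the trial has 55-64% power rather than 80%. The documents do not support that. Those two values come from conventions A and B at one assumed exposure of 6.5 months; across 5 to 8 months the same two conventions span 45-70%. Under C and D, power for 1.6 versus 0.6 is about 73-89%, a range that includes the plan's figure. The Data Analysis Plan names logistic models with a random intercept and supplies no count variance that would settle the choice.

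Even pro-rating is also likely to be pessimistic. The observation window covers the October-March respiratory season defined in the Overview, and no in-season rate is given. Seasonality reduces the loss to a degree that depends on the convention. If 70% or 90% of a year's encounters fell inside a child's window, B would give 0.72 or 0.78, and it returns to 0.81 only at 100%. Under C, a 60% share already gives 0.84. If the SD came from season-length data expressed per year, little or no correction would be due.

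A second tempting inference is that short observation causes the low power for a 20% reduction. It does not: a full year already gives only 15-16% on the two-mean calculations.

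Finally, the trial is called a pilot and will report credible intervals and a probability of benefit, and nothing in the plan says that a null result would be taken to exclude a 20% effect. That limits the harm. These objections stand against any single corrected figure. They do not supply the missing exposure basis, and they leave the 20% result and the 38% label untouched.

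**Conclusion.** The point holds in this form. The stated 80% is a full-year figure applied to a 5 to 8 month outcome, without saying so. Whether power for 1.6 versus 0.6 is really below 80% is conditional on the variance model, the seasonal rate and the period behind the SD, none of which the plan states.

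Two things do not depend on that choice. Power for the plan's own expected 20% reduction is about 9-14% under all four scalings, mainly because the sample was sized for an effect about three times as large (62.5/20 = 3.1). And the 38% label contradicts the rates printed beside it. The paragraph should be corrected, but it should not be replaced by another single power figure resting on unstated assumptions.

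**What to change.** Rewrite the Sample size and power section to:

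- state the period over which the SD of 1.66 was observed;
- give the expected encounters per child over the planned 5 to 8 months, preferably from in-season clinic data;
- name the variance model used, for example a negative binomial rate ratio with a log person-time offset;
- reconcile 1.6 versus 0.6, 38% and 20% into one target effect;
- restate power on that basis for that target and, beside it, for the 20% reduction;
- say that a non-significant result does not rule out a 20% reduction.

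The cost is one rewritten paragraph and a look at the clinic data behind the rate. No patients are added. The price is a less favourable stated power for the expected effect; for 1.6 versus 0.6 the restated figure could fall on either side of 80%.

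### The power statement equates 1.6 vs 0.6 encounters with a 38% reduction; it is 62.5%, and 90 children give about 40% power for 38% and about 15% for the expected 20%

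*Combined protocol and SAP*

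**What the plan says.** The section Sample size and power sets out the inputs. For the control rate: "we expect the control group to have 1.6 encounters per child-year (SD=1.66", with the bracket closing after the SD. For the test: "Assuming a two-sided alpha = 0.05". For size and power: "a sample size of 90 (45/group) will have 80% power". For the effect: "to detect a difference of 1 in the encounter rate between placebo and azithromycin groups". It then restates that effect in brackets as "i.e., 1.6 vs 0.6 in encounter rate or 38% reduction".

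Study Outcomes item 1 gives another effect for the same kind of encounter: "we expect a 20% total reduction in face to face encounters". No power is stated for it.

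Allocation is equal (Study Procedures: "Half of the patients will receive azithromycin"), and the Overview plans slightly more children than the power section: "This pilot randomized control trial (RCT) will enroll 92 children", which is 46 per group.

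**The concern.** One sentence presents two different effects as one. The absolute difference of 1 and the pair 1.6 vs 0.6 agree with each other, but the percentage beside them does not. The plan also expects a 20% reduction elsewhere, so three effect sizes (62.5%, 38% and 20%) stand for one outcome and are never reconciled.

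The percentage is what many readers will take away. On its face, the trial is well powered for a reduction of just over one third. The section adds that power is more limited for secondary outcomes, which suggests that power for the primary outcome is adequate. If the 80% in fact belongs to a much larger reduction, a non-significant result could be read as evidence against a 38% or 20% benefit when the design had little chance of showing either.

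**Working it through.** **Inputs.** From Sample size and power: control rate 1.6 per child-year, SD 1.66, two-sided alpha 0.05, 45 per group. From Study Outcomes item 1: a 20% reduction. The section names no test. A two-sample comparison of means with a common SD is assumed, because it reproduces the plan's figure.

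**Step 1: the percentage.**
- Reduction from 1.6 to 0.6: (1.6 − 0.6)/1.6 = 62.5%.
- Share of encounters that remains: 0.6/1.6 = 37.5%. This may be where 38% came from, but the documents do not say.
- A 38% reduction from 1.6: 0.38 × 1.6 = 0.608, giving 1.6 vs 0.992. At exactly 37.5% the difference is 0.6, giving 1.6 vs 1.0.
- A 20% reduction from 1.6: 0.20 × 1.6 = 0.32, giving 1.6 vs 1.28.

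**Step 2: reproduce the stated 80%.** The standard error of the difference is 1.66 × √(2/45) = 0.350. For a difference of 1.0 the noncentrality is 1.0/0.350 = 2.857. Against the two-sided 5% critical value of t with 88 degrees of freedom (1.987), power is 80.7%. The normal approximation gives 81.5%. The stated 80% is therefore right for a difference of 1.0.

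**Step 3: the same calculation for the other effects** (t-test, common SD 1.66):

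| Difference | Rates | Reduction | Power, 45/group | Power, 46/group | n/group for 80% |
|---|---|---|---|---|---|
| 1.0 | 1.6 vs 0.6 | 62.5% | 80.7% | 81.5% | 45 |
| 0.608 | 1.6 vs 0.992 | 38% | 40.5% | 41.2% | 118 |
| 0.6 | 1.6 vs 1.0 | 37.5% | 39.6% | 40.3% | 122 |
| 0.32 | 1.6 vs 1.28 | 20% | 14.8% | 15.0% | 424 |

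**Step 4: smallest difference with 80% power at 45 per group.** By the normal approximation, (1.960 + 0.842) × 0.350 = 0.98, or 61% of 1.6. By the t-test it is 0.99, and 0.99/1.6 = 62%.

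**Step 5: sensitivity to the common SD.** Counts usually have a smaller SD when the mean is lower. As an assumption not in the documents, take a negative binomial model whose dispersion matches mean 1.6 and SD 1.66: (1.66² − 1.6)/1.6² = 0.45. A log-rate-ratio test with 45 per group then gives:

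| Follow-up | Power for 62.5% | Power for 38% | Power for 20% |
|---|---|---|---|
| 12 months | 96% | 52% | 16% |
| 8 months | 88% | 42% | 14% |
| 5 months | 74% | 31% | 11% |

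The rows for 5 and 8 months span the primary aim's window (3 to 6 months of treatment plus 2 months). Under this model too, power stays far below 80% for 38% and for 20%.

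**The case against.** The strongest reply is that the core of the power statement is sound. Alpha, SD, sample size, the difference of 1 and both rates all agree and give 80.7%; only one bracketed percentage is wrong. The rates are printed next to it, so a careful reader has the true effect in view, and the slip changes neither the sample size nor the analysis. That is correct as far as it goes. The impossibility lies in pairing 1.6 vs 0.6 with 38%, not in 80% power for a difference of 1. But the sentence does attach the 80% to a 38% reduction, and that claim is wrong by about half.

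Second, the 20% is an expectation, and the plan never claims power for it. That also stands: the gap between expected and detectable effect is a design weakness, not a slip in arithmetic. It still belongs here, because once the percentage is corrected nothing tells the reader that power at the expected effect is about 15%.

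Third, the trial is called a pilot, and the Data Analysis Plan promises credible intervals and a probability of benefit, so interpretation will not rest on a p-value alone. This reduces the risk of misreading a null result and may justify a small sample. It does not make the percentage right.

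Fourth, the 40% and 15% rest on a t-test with a common SD on a full-year scale. The Data Analysis Plan names logistic regression with a random intercept, and the primary window is 5 to 8 months. This is a fair limit on the precision of those figures, and any that are added should carry their assumptions. The sensitivity results do not rescue 80% for either effect.

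**Conclusion.** The concern holds. The percentage in the trial's only power statement is wrong as written: 1.6 vs 0.6 is a 62.5% reduction. The stated 80% power belongs to that reduction. For a 38% reduction the trial would miss a true effect about 60% of the time, and for the expected 20% about 85% of the time.

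The 62.5% follows from the two printed rates alone. The power figures assume a two-sample t-test, a common SD of 1.66 per child-year, two-sided alpha 0.05 and 45 per group. Using 46 per group changes them by less than one percentage point. Under the assumed negative binomial model the ranges are about 31% to 52% for a 38% reduction and 11% to 16% for 20%.

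The documents do not prove which number slipped. However, 1.6 is given as the control rate and repeated in the comparison, and the difference of 1 reproduces the stated power, so correcting the percentage is the reading that fits the text.

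**What to change.** In Sample size and power, replace the sentence on power with wording to this effect:

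> With 45 children per group, two-sided alpha 0.05 and a common SD of 1.66, a two-sample t-test has 80% power for a difference of 1.0 encounter per child-year (1.6 vs 0.6, a 62.5% reduction). On the same assumptions, power is about 40% for a 38% reduction and about 15% for the 20% reduction in Study Outcomes item 1.

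In Study Outcomes item 1, add a cross-reference to this statement, and say that an inconclusive result would not rule out a 20% effect.

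The cost is protocol wording only. No extra children and no change to the design are requested. The price is a less favourable statement of what the trial can detect: about 62% rather than 38%.
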